#### **8.4.3. Serious Adverse Events**

An AE (including a solicited AR) is considered a SAE if it results in any of the following outcomes:

- **Death**

A death that occurs during the study or that comes to the attention of the Investigator during the protocol-defined follow-up period must be reported to the Sponsor, whether or not it is considered related to the study intervention.

- **Is life-threatening**

An AE is considered life-threatening if, in the view of either the Investigator or the Sponsor, its occurrence places the participant at immediate risk of death. It does not include an AE that, had it occurred in a more severe form, might have caused death.

- **Inpatient hospitalization or prolongation of existing hospitalization**

In general, inpatient hospitalization indicates the participant was admitted to the hospital or emergency ward for at least 1 overnight stay as an inpatient for observation and/or treatment that would not have been appropriate in the physician's office or outpatient setting. Complications that occur during inpatient hospitalization will be recorded as an AE; however, if a complication/AE prolongs hospitalization or otherwise fulfills SAE criteria, the complication/AE will be recorded as a separate SAE.

- **Persistent or significant disability or substantial disruption of the ability to conduct normal life functions**

This definition is not intended to include experiences of relatively minor medical significance such as uncomplicated headache, nausea/vomiting, diarrhea, influenza, and

accidental trauma (eg, sprained ankle) which may interfere with or prevent everyday life functions but do not constitute a substantial disruption.

- **Congenital anomaly or birth defect**
- **Medically important event**

An AE is medically important if, per the medical judgment of the Investigator or the Sponsor, it is determined that SAE reporting is appropriate in other situations, such as important medical events that may not be immediately life-threatening or result in death or hospitalization, but may jeopardize the participant or require medical or surgical intervention to prevent one of the other outcomes listed in the above definition.

#### **8.4.4.     Solicited Adverse Reactions**

Solicited ARs are a subset of AEs consisting of selected signs and symptoms that participants are asked to record/report. In this study, the solicited ARs are reactogenicity events. The term “reactogenicity” refers to the occurrence of transient adverse effects associated with administration of study intervention. An eDiary will prompt daily participant reporting of solicited ARs. Participants will record such occurrences in the eDiary on the day of administration of study intervention and on each of the 6 days after dosing.

Severity grading of reactogenicity events will be automatically assigned upon participant entry into the eDiary based on the grading scales presented in [Table 7](#), which are modified from the Toxicity Grading Scale for Healthy Adult and Adolescent Volunteers Enrolled in Preventive Vaccine Clinical Trials ([DHHS 2007b](#)). All solicited ARs (local and systemic) will be considered causally related to dosing.

If a participant reports a solicited AR with onset during the solicited period, but they did not record the event in the eDiary, then the event should be recorded by study site staff in the EDC.

If the event starts during the solicited period, but continues beyond 7 days after dosing, the participants should notify the site to provide an end date and close out the event in the EDC.

If the participant reported an event that started after the solicited period (ie, after Day 7), it should be recorded as an AE in the EDC. Causality for these events will be determined per assessment by the Investigator.

Any solicited AR that meets any of the following criteria must be entered into the participant’s source document and must also be recorded by the study site staff in the EDC:

- Solicited AR that results in a visit to a HCP (MAAE).
- Solicited AR leading to the participant withdrawing from the study or the participant being withdrawn from the study by the Investigator (AE leading to discontinuation).
- Solicited AR lasting beyond 7 days post injection.
- Solicited AR that otherwise meets the definition of an SAE.

**Table 7:      Solicited Adverse Reactions and Grades**

Reaction	Grade 0 (None)	Grade 1 (Mild)	Grade 2 (Moderate)	Grade 3 (Severe)	Grade 4a (Life- Threatening)
Local					
Injection site pain	None	No interference with activity	Some interference with activity	Prevents daily activity	Requires emergency room visit or hospitalization
Injection site erythema (redness)	<25 mm/ <2.5 cm	25-50 mm/ 2.5-5 cm	51-100 mm/ 5.1-10 cm	>100 mm/ >10 cm	Necrosis or exfoliative dermatitis
Injection site swelling/induration (hardness)	<25 mm/ <2.5 cm	25-50 mm/ 2.5-5 cm	51-100 mm/ 5.1-10 cm	>100 mm/ >10 cm	Necrosis
Axillary (underarm) swelling or tenderness ipsilateral to the side of injection	None	No interference with activity	Some interference with activity	Prevents daily activity	Requires emergency room visit or hospitalization
Systemic					
Headache	None	No interference with activity	Some interference with activity	Prevents daily activity	Requires emergency room visit or hospitalization
Fatigue	None	No interference with activity	Some interference with activity	Prevents daily activity	Requires emergency room visit or hospitalization
Myalgia (muscle aches all over body)	None	No interference with activity	Some interference with activity	Prevents daily activity	Requires emergency room visit or hospitalization

Reaction	Grade 0 (None)	Grade 1 (Mild)	Grade 2 (Moderate)	Grade 3 (Severe)	Grade 4 a (Life-Threatening)
Arthralgia (joint aches in several joints)	None	No interference with activity	Some interference with activity	Prevents daily activity	Requires emergency room visit or hospitalization
Nausea/vomiting	None	No interference with activity or 1-2 episodes/24 hours	Some interference with activity or >2 episodes/24 hours	Prevents daily activity, requires outpatient intravenous hydration	Requires emergency room visit or hospitalization for hypotensive shock
Chills	None	No interference with activity	Some interference with activity not requiring medical intervention	Prevents daily activity and requires medical intervention	Requires emergency room visit or hospitalization
Fever (oral)	<38.0°C <100.4°F	38.0–38.4°C 100.4–101.1°F	38.5–38.9°C 101.2–102.0°F	39.0–40.0°C 102.1–104.0°F	>40.0°C >104.0°F

Note: Events listed above but starting >7 days post study intervention will be recorded in EDC. Causality for each event reported in EDC will be determined per assessment by the Investigator.

a Grading of Grade 4 events will be determined per Investigator and assessment is recorded in EDC.

Source: Guidance for Industry – Toxicity Grading Scale for Healthy Adult and Adolescent Volunteers Enrolled in Preventive Vaccine Clinical Trials ([DHHS 2007b](#)).

#### 8.4.5. Medically Attended Adverse Events

A MAAE is an AE that leads to an unscheduled visit to an HCP. This would include visits to a study clinic for unplanned assessments (eg, rash assessment, abnormal laboratory follow-up) and visits to HCPs external to the study clinic (eg, emergency room, urgent care, primary care physician). Investigators will review unsolicited AEs for the occurrence of any MAAEs. Unsolicited AEs will be captured in EDC.

An unscheduled visit for assessment of protocol-defined ILI (symptoms assessment and NP swab) is not considered a MAAE unless additional medical evaluation, including examinations/testing not required per protocol, and/or treatment is provided during the visit.

#### 8.4.6. Adverse Events of Special Interest

An AESI is an AE (serious or nonserious) of scientific and medical concern specific to the Sponsor's product or program, for which ongoing monitoring and immediate notification by the

Investigator to the Sponsor are required. Such events may require further investigation to characterize and understand them.

In addition to anaphylaxis and myocarditis/pericarditis, AESIs for this protocol (thrombocytopenia and new onset of or worsening of neurologic diseases) are described in [Section 11.3](#).

All AESIs will be collected through the entire study period and must be reported to the Sponsor or designee immediately and in all circumstances within 24 hours of becoming aware of the event via EDC. If a site receives a report of a new AESI from a participant or receives updated information on a previously reported AESI at a time after the eCRF has been taken offline, then the site should report this information on the paper SAE/AESI Report Form provided to the study site via e-mail or fax as provided on the form ([Section 8.2.9](#)).

#### 8.4.6.1. Anaphylaxis

All suspected cases of anaphylaxis associated with study intervention administration should be recorded as AESIs, reported as an SAE, based on the criteria for a medically important event, unless the event meets other serious criteria. As an AESI and/or SAE, the event should be reported to the Sponsor or designee immediately and in all circumstances within 24 hours, per [Section 8.2.9](#). The Investigator will submit any updated anaphylaxis case data to the Sponsor within 24 hours of it being available. For reporting purposes, a participant who displays signs or symptoms consistent with anaphylaxis (as below) should be reported as a potential case of anaphylaxis. This is provided as general guidance for Investigators and is based on the Brighton Collaboration case definition ([Rüggeberg et al 2007](#)).

Anaphylaxis is an acute hypersensitive reaction with multi-organ system involvement that can present as, or rapidly progress to, a severe life-threatening reaction. It may occur following exposure to allergens from a variety of sources.

Anaphylaxis is a clinical syndrome characterized by the following:

- Sudden onset AND
- Rapid progression of signs and symptoms AND
- Involves 2 or more organ systems, as follows:
  - **Skin/mucosal:** urticaria (hives), generalized erythema, angioedema, generalized pruritus with skin rash, generalized prickle sensation, red and itchy eyes.
  - **Cardiovascular:** measured hypotension, clinical diagnosis of uncompensated shock, loss of consciousness or decreased level of consciousness, evidence of reduced peripheral circulation.
  - **Respiratory:** bilateral wheeze (bronchospasm), difficulty breathing, stridor, upper airway swelling (lip, tongue, throat, uvula, or larynx), respiratory distress, persistent dry cough, hoarse voice, sensation of throat closure, sneezing, rhinorrhea.
  - **Gastrointestinal:** diarrhea, abdominal pain, nausea, vomiting.

#### **8.4.6.2. Myocarditis/Pericarditis**

A case of suspected, probable, or confirmed myocarditis, pericarditis, or myopericarditis should be reported as an AESI, even if it does not meet criteria per the CDC Working Case Definitions. The event should also be reported as an SAE if it meets seriousness criteria (see [Section 8.2.9](#)).

An independent CEAC will review reported cases of myocarditis, pericarditis, and myopericarditis to determine if they meet CDC criteria for “probable” or “confirmed” events ([Section 8.5.2](#)).

The CDC Working Case Definitions are provided in [Section 11.4](#) as guidance.

#### **8.4.7. Assessment of Intensity/Severity**

An event is defined as “serious” when it meets at least one of the predefined outcomes as described in the definition of an SAE ([Section 8.4.3](#)), NOT when it is rated as severe.

The severity (or intensity) of an AR or AE refers to the extent to which it affects the participant’s daily activities. The Toxicity Grading Scale for Healthy Adult and Adolescent Volunteers Enrolled in Preventive Vaccine Clinical Trials ([DHHS 2007b](#)) will be used to categorize local and systemic reactogenicity events (solicited ARs), clinical laboratory test results, and vital sign measurements observed during this study. Specific criteria for local and systemic reactogenicity events are presented in [Section 8.4.4](#).

The determination of severity for all unsolicited AEs should be made by the Investigator based upon medical judgment and the definitions of severity as follows:

- Mild: These events do not interfere with the participant’s daily activities.
- Moderate: These events cause some interference with the participant’s daily activities and require limited or no medical intervention.
- Severe: These events prevent the participant’s daily activity and require intensive therapeutic intervention.

Study site staff should elicit from the participant the impact of AEs on the participant’s activities of daily living to assess severity and document appropriately in the participant’s source documentation. An AE characterized as intermittent requires documentation of onset and duration of each episode. An AE that fluctuates in severity during the course of the event is reported once in the eCRF at the highest severity observed.

#### **8.4.8. Assessment of Causality**

The Investigator will assess causality (ie, whether there is a reasonable possibility that the study intervention caused the event) for all AEs and SAEs. The relationship will be characterized using the following classification:

- **Not related:** There is not a reasonable possibility of a relationship to the study intervention. Participant did not receive the study intervention OR temporal sequence of the AE onset relative to administration of the study intervention is not reasonable OR the AE is more likely explained by another cause than the study intervention.

- **Related:** There is a reasonable possibility of a relationship to the study intervention. There is evidence of exposure to the study intervention. The temporal sequence of the AE onset relative to the administration of the study intervention is reasonable. The AE is more likely explained by the study intervention than by another cause.

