### **8.2.9. Reporting Serious Adverse Events**

Any AE considered serious by the Investigator or that meets SAE criteria ([Section 8.4.3](#)) must be reported to the Sponsor immediately (within 24 hours of becoming aware of the SAE). The Investigator will assess whether there is a reasonable possibility that the study intervention caused the SAE. The Sponsor will be responsible for notifying the relevant regulatory authorities of any SAE as required per applicable regulations. The Investigator is responsible for notifying the IRB or IEC directly.

If the eCRF is unavailable at the time of the SAE, the paper SAE/AESI Report Form distributed to the study sites should be completed and sent via e-mail or fax as provided on the form.

Regulatory reporting requirements for SAEs are described in [Section 8.4.9](#).

The Investigator and any qualified designees are responsible for detecting, documenting, and recording events that meet the definition of an AE, including SAEs, and remain responsible for following up AEs that are serious, considered related to the study intervention or study procedures, or that caused the participant to discontinue the study.

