6.4.2.1. Overview of Unsolicited TEAEs

An overall summary of TEAEs up to 28 days after study vaccination will include the number and percentage of participants, along with the number of events, by vaccination group who experience the following:

- Any TEAEs
- Any serious TEAEs
- Any non-serious TEAEs
- Any non-serious TEAEs severe/Grade 3 or higher
- Any AESIs
- Any treatment-emergent MAAEs
- Any TEAEs leading to discontinuation from participation in the study
- Any severe/Grade 3 or higher TEAEs
- Any TEAEs that are fatal

The table will also include the number and percentage of participants with TEAEs that are treatment-related in each of the above categories.

The above summary will be repeated on all reported events up to EoS.

In addition, separate listings for TEAEs leading to discontinuation from participation in the study, SAEs, treatment-related SAEs, and treatment-emergent MAAEs will be provided. Listings of deaths including cause of death and TEAEs in participants who died will also be provided.

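### Protocol section 8.4.8 asks one causality question but scores it by another, so a reasonably possible event with a likelier rival cause is scored Not related and a tie has no category

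*Protocol*

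**What the plan says.** Protocol section 8.4.8 tells the investigator to judge, for every AE and SAE, "whether there is a reasonable possibility that the study intervention caused the event". It then gives a two-level scale.

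- **Not related** opens with "There is not a reasonable possibility of a relationship to the study intervention". Three conditions joined by OR follow: no exposure, implausible timing, or "the AE is more likely explained by another cause than the study intervention".
- **Related** opens with "There is a reasonable possibility of a relationship to the study intervention". Exposure and plausible timing follow as further statements, and the entry ends with "The AE is more likely explained by the study intervention than by another cause". No OR separates these statements.

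For SAEs, Protocol section 8.2.9 puts the question without any comparison of causes: "The Investigator will assess whether there is a reasonable possibility that the study intervention caused the SAE".

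The SAP never defines treatment-related, so section 8.4.8 is the only definition available. SAP section 6.4.2.1 reports the "number and percentage of participants with TEAEs that are treatment-related in each of the above categories". SAP section 6.4.2.2 adds related-only tables for TEAEs, AESIs, SAEs, severe TEAEs and MAAEs, and section 6.4.2.4 adds related TEAEs by maximum severity.

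**The concern.** A cause can be a reasonable possibility without being the likeliest one. The section's question and its category text therefore set different thresholds, and an investigator who follows one can reach a different answer from an investigator who follows the other.

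Such cases will plausibly occur here. Participants are 50 to 75 years old, and Protocol section 5.2 admits stable conditions such as mild hypertension. Suppose palpitations start on Day 6 in a participant with controlled hypertension. Palpitations are not a solicited reaction, so causality is left to the investigator. If the investigator thinks the vaccine a reasonable possibility but the background condition likelier, the opening question makes the event related and the OR condition makes it not related.

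At stake is the meaning of every treatment-related line in the safety tables. Also at stake is any safety reporting that rests on the investigator's causality call, such as the reports of suspected unexpected serious adverse reactions in Protocol section 8.4.9.

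**Working it through.** The plan states no figure on this point, so the main check is one of wording.

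**Step 1: apply each text to the possible cases.** Exposure and plausible timing are taken as satisfied.

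| Investigator's view | Opening question of 8.4.8, and 8.2.9 | All statements of Related | Not related | Outcome on the category text |
|---|---|---|---|---|
| Reasonable possibility, vaccine likelier | Related | Met | Not met | Related |
| Reasonable possibility, rival likelier | Related | Last statement fails | Third OR condition met, but the category's opening sentence is untrue | Not related, or neither if the opening sentence is enforced |
| Reasonable possibility, equally likely | Related | Last statement fails | Opening sentence untrue, no OR condition met | No category |
| No reasonable possibility | Not related | Fails | Opening sentence met | Not related |

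The two texts part company in rows 2 and 3.

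**Step 2: direction.** Let A be the events that satisfy the opening question and B the events that satisfy every statement of Related. The opening statement of Related is that same question, so B lies inside A. The count of B cannot exceed the count of A and is smaller whenever a row 2 or row 3 event occurs. If f is the share of A in which the vaccine is not the likelier cause, then B = (1 − f) × A.

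**Step 3: size.** The documents do not give f or anything from which it could be derived. What follows shows scale only, on assumed values. It uses the formula behind Protocol Table 8, P(at least 1) = 1 − (1 − p)^n. With n = 100 and p = 3% this gives 1 − 0.97^100 = 95.2%, as the table states. Now assume that 3% of an arm have one reasonably possible unsolicited event each, and that every site follows the category text literally:

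| Assumed f | Expected related participants per 100 | P(at least 1 related) |
|---|---|---|
| 0 | 3.0 | 95.2% |
| 10% | 3.0 × 0.90 = 2.7 | 1 − 0.973^100 = 93.5% |
| 25% | 3.0 × 0.75 = 2.25 | 1 − 0.9775^100 = 89.7% |
| 50% | 3.0 × 0.50 = 1.5 | 1 − 0.985^100 = 77.9% |

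The row f = 0 also describes investigators who answer only the opening question, whatever the mix of causes.

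**Step 4: reach.**

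- *Affected:* unsolicited AEs, SAEs, MAAEs and AESIs judged by the investigator. By Protocol section 8.4.4 this includes solicited-type symptoms that start after Day 7.
- *Not affected, solicited reactions:* "All solicited ARs (local and systemic) will be considered causally related to dosing".
- *Not affected, primary endpoints:* Protocol Table 2 and SAP section 3.1 count events without reference to relationship.
- *Not affected, pause rules:* Protocol Tables 4 and 5 use their own attribution wording and do not refer to this scale.
- *Not affected, notification of the sponsor:* Protocol sections 8.2.9 and 8.4.6 send SAEs and AESIs to the sponsor within 24 hours whatever the causality.

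**The case against.** The best defence is that the later sentences in each category are working criteria for its opening sentence. On that view, an event better explained by something else is simply what this protocol means by no reasonable possibility. Row 2 is then Not related without conflict, and section 8.2.9 only repeats a question that section 8.4.8 goes on to define. This is a possible reading, and it is fair to say that section 8.2.9 sets up no rival scale. But the reading works only by making reasonable possibility mean likeliest cause, which neither section says, and it still leaves the tie without a category.

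A second defence is that the consequences are small, and much of this stands. One definition applies to all seven randomized arms, the study tests no hypothesis, and all AEs are recorded whatever their relationship (Protocol section 8.2.8). No mechanism for a difference between arms is apparent. Site training and eCRF guidance, which are not among the documents, may already settle the matter.

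A reader might go further and infer that the cut-off is a 50% probability. The text does not say so. It compares the vaccine with another cause, and among three candidates at 40%, 30% and 30% the vaccine would be the likeliest while still below 50%.

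**Conclusion.** The inconsistency holds as a defect of wording in Protocol section 8.4.8. Read literally, the category text scores as Not related some events that meet the section's own question, and it leaves ties unclassified. Measured against that question, the effect on the related count has one direction, downward. Its size cannot be computed; the illustration above rests on an assumed 3% rate, an assumed f and literal reading at every site.

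Three stronger conclusions are tempting and are not supported:

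- *That related events will in fact be under-counted, or that many will be.* This depends on how investigators read the section and on f, and neither is known.
- *That related counts from different sites could not be pooled.* Different readings could blur the absolute percentages, but nothing in the documents shows that pooling would be invalid.
- *That the primary safety results are compromised because safety is the primary objective.* The primary endpoint counts ignore relationship. Only the treatment-related subsets and causality-dependent reporting are exposed.

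The point is worth correcting because the correction is simple, but it does not threaten the study's main results.

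**What to change.** Use the one test the protocol already states. In section 8.4.8, define Related as a reasonable possibility, with exposure and plausible timing, and define Not related as no reasonable possibility. Lack of exposure and implausible timing can stay as reasons for the latter. Remove both clauses that compare the vaccine with another cause. Every event then has exactly one category, and section 8.4.8 agrees with section 8.2.9. Mirror the wording in any eCRF completion guidance, and have the SAP cite section 8.4.8 as its definition of treatment-related.

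The sponsor could instead keep the comparative test and add a rule for ties, but it would then have to reword the opening of section 8.4.8 and section 8.2.9 to match. Removing the clauses is the smaller edit.

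The cost is a protocol wording change and matching guidance, with no effect on sample size, visits or analysis methods. The downside is that the reported share of treatment-related events may be somewhat higher.
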